## 2. STATISTICAL HYPOTHESES

The study is designed to test the superiority of mepolizumab 100mg SC vs. placebo in both co-primary efficacy endpoints of total endoscopic nasal polyp score at Week 52 and nasal obstruction VAS score during the 4 weeks prior to Week 52. Each co-primary endpoint will be tested at the two-sided 5% alpha level (one-sided 2.5%) and both tests are required to be significant to achieve the primary objective of the study.

### 2.1. Multiplicity Adjustment

Multiplicity arising from the multiple secondary endpoints will be controlled using the closed testing procedure specified below for strong control of type I error. Hypotheses associated with the two primary ( $H_1$  and  $H_2$ ) and six secondary endpoints ( $H_3$  to  $H_8$ ) will be tested using a gatekeeping procedure based on the graphical approach to sequentially rejective multiple test procedures [Bretz, 2009]. The two primary hypotheses  $H_1$  and  $H_2$  will each be tested first and will be allocated the level  $\alpha$ , where  $\alpha = 0.05$  (two-sided). If these are both rejected at level  $\alpha$ , the procedure then is as follows: the hypotheses  $H_i$ ,  $i = 3, \dots, 8$  are tested each at its local significance level  $\alpha_i$ . If a hypothesis  $H_i$  can be rejected, its level is reallocated to one of the other hypotheses according to the pre-specified rules represented by [Figure 1](#). The reallocation weights are updated in the reduced graph and the testing step repeated for the remaining, non-rejected hypotheses with the updated local significance levels. This possibly leads to further rejected null hypotheses with associated reallocation of the local significance levels. The procedure is repeated until no further hypothesis can be rejected. The reallocation of the local alpha levels is fully determined by the initial graph ([Figure 1](#)) and the update algorithm described by [Bretz, 2009].

**Figure 1 Multiplicity Testing Strategy Across Primary and Secondary Endpoints**

**Primary:**

$H_1$ : Total Endoscopic Nasal Polyps score at Week 52

$H_2$ : Nasal Obstruction VAS score during the 4 weeks prior to Week 52

**Secondary:**

$H_3$ : Overall VAS score during the 4 weeks prior to Week 52

$H_4$ : Lund Mackay CT score at Week 52

$H_5$ : Composite VAS score of Nasal Symptoms during the 4 weeks prior to Week 52

$H_6$ : SNOT-22 Total score at Week 52

$H_7$ : Loss of smell VAS score during the 4 weeks prior to Week 52

$H_8$ : Time to First Nasal Surgery or course of systemic CS for CRSwNP / ECRS up to Week 52

where  $\epsilon$  reflects an infinitesimally small value, indicating the potential for alpha to be reallocated dependent on the rejection of all previous tests

For the initial graph (Figure 1) the resulting test procedure can be summarized as follows: If both co-primary endpoints ( $H_1$  and  $H_2$ ) are rejected, the first two secondary endpoints (Overall VAS Symptom Score [ $H_3$ ] and Lund Mackay CT score [ $H_4$ ]) will each be tested at a significance level of  $\alpha/2$  (0.025). If either endpoint is rejected at the  $\alpha/2$  (0.025) level, the  $\alpha/2$  (0.025) from that given endpoint will be reallocated and re-used within the subsequent test of the next secondary endpoint according to the pre-specified rules represented by Figure 1.

- If the Overall VAS score endpoint ( $H_3$ ) endpoint is rejected at the  $\alpha/2$  (0.025) level, the Composite VAS score of Nasal Symptoms ( $H_5$ ) and SNOT-22 total score ( $H_6$ ) will then also be tested. Only following rejection of both endpoints ( $H_5$  and  $H_6$ ) will the Loss of Smell VAS symptom endpoint ( $H_7$ ) be tested.
- If able to reject the loss of smell VAS endpoint ( $H_7$ ), the  $\alpha/2$  level from this endpoint will be reallocated to the testing of the Lund Mackay CT score ( $H_4$ ), to allow a test at a full level of  $\alpha$ , if not already rejected at the  $\alpha/2$  significance level.
- Only following rejection of all other secondary endpoints ( $H_3$  to  $H_7$ ), will the final secondary endpoint of Time to First Nasal Surgery or course of systemic CS for CRSwNP / ECRS ( $H_8$ ) be tested.

Lund Mackay CT score ( $H_4$ ) is an important endpoint in the clinical practice of Japan and China, however, has not been studied previously within the mepolizumab clinical development program. The above testing strategy demonstrates the importance of this endpoint, whilst permitting testing of other secondary endpoints if not initially rejected at a significance level of  $\alpha/2$ . The Composite VAS of Nasal Symptoms, SNOT-22 and Loss of Smell VAS secondary endpoints are all correlated patient reported endpoints measuring improvements in symptoms; these endpoints are grouped within the above strategy for testing in sequence following the rejection of the Overall VAS Score ( $H_3$ ) to increase power across these symptom endpoints. If all symptom endpoints ( $H_3, H_5, H_6, H_7$ ) are rejected, the above strategy permits a test of the Lund Mackay CT score ( $H_4$ ) at a full level of  $\alpha$ , if not already rejected at the initial  $\alpha/2$  significance level.

For secondary endpoints unadjusted p-values and p-values adjusted for multiplicity, based on the above hierarchy, will be presented. Adjusted p-values will be calculated using the gMCP package within R TM.

### 3. ANALYSIS SETS

Analysis Set	Definition / Criteria	Analyses Evaluated
All Participants Enrolled	
 
• All participants enrolled and for whom a record exists on the study database
 
	
 
• Study Population
 

Randomised	
 
• All participants who were randomly assigned to study treatment in the study
 
• Any participant who receives a treatment randomisation number will be considered to have been randomised
 
	
 
• Study Population
 

Intent-to-Treat (ITT)	
 
• All randomised participants who receive at least 1 dose of study treatment
 
• Participants will be analysed according to the treatment they are allocated at randomisation
 
	
 
• Efficacy
 

Safety	
 
• All randomised participants who receive at least 1 dose of study treatment
 
• Participants will be analysed according to the treatment they actually received for more than 50% of treatment administrations
 
	
 
• Safety
 

Pharmacokinetic (PK)	
 
• All participants in the Safety analysis set who have at least 1 non-missing PK assessment (Non-quantifiable [NQ] values will be considered as non-missing values).
 
• Participants will be analysed according to the treatment they actually received for more than 50% of treatment administrations
 
	
 
• PK
 

**Note:** "Enrolled" means a participant's, or their legally acceptable representative's (LAR's), agreement to participate in a clinical study following completion of the informed consent process.

## 4. STATISTICAL ANALYSES

### 4.1. General Considerations

#### 4.1.1. General Methodology

The Intent-to-Treat (ITT) analysis set will be used for all Study Population analyses and Efficacy analyses, and the Safety analysis set will be used for all Safety analyses.

In the case of wrong stratification assigned at the time of randomisation, the analyses will be performed based on the data collected in the eCRF, not the assigned stratum at randomisation.

Confidence intervals will use 95% confidence levels unless otherwise specified.

Unless otherwise specified, continuous data will be summarized using descriptive statistics: n, mean, standard deviation (SD), median, minimum and maximum.

Categorical data will be summarized as the number and percentage of participants in each category.

#### 4.1.2. Baseline Definition

##### 4.1.2.1. Visit-Based Endpoints

For all visit-based endpoints, including the co-primary endpoint of endoscopic NP score, Baseline will be defined as the latest non-missing measurement collected prior to the first dose of study treatment. This will generally be from the Day 1 (Visit 2) assessment but may be from an unscheduled assessment. Where time is collected, an assessment is valid for use as Baseline if the date and time is prior to or the same as the date and time of first dose. Where time is not collected, an assessment is valid for use as Baseline if the date of assessment is on or before the date of first dose.

Unless otherwise stated, if baseline data is missing no derivation will be performed and baseline will be set to missing.

##### 4.1.2.2. eDiary Data

Participants will report daily on the severity of individual and overall NP symptoms using an eDiary; this includes information for the co-primary endpoint of mean nasal obstruction VAS score. The baseline value for endpoints reported in the eDiary will be determined as the average score from the 7 days of diary data collected prior to Day 1 (using non-missing data recorded between Day -7 and Day -1 inclusive). Participants are required to have at least 4 days of non-missing diary data available within the baseline period (7 days prior to Day 1) to meet the necessary study randomisation criteria.

#### 4.1.3. Multicentre Studies

In this multicentre global study, the number of enrolled participants and the number randomised to each treatment arm will be presented by centre and country. Separate subgroup analyses will be performed by country (as detailed in Section 4.11.1).

The study will be randomised separately for each country; therefore country will be included as a fixed effect covariate in the analysis models for all efficacy endpoints. Small numbers of participants in a treatment group within a country may result in model

convergence issues, in these cases further combining of countries may be considered or exclusion of the country covariate if required.

## 4.2. Co-primary Endpoints Analyses

### 4.2.1. Definition of Endpoint(s)

The co-primary endpoints for analysis are:

- Change from baseline in total endoscopic nasal polyp score at Week 52 (based on centrally read data)
- Change from baseline in mean nasal obstruction VAS score during the 4 weeks prior to Week 52

#### 4.2.1.1. Total Endoscopic NP Score

Total endoscopic nasal polyp score is collected at clinical visits. Independent reviewers, blinded to treatment, grade the total endoscopic nasal polyp score from image recording of endoscopies. The total score is reported as the sum of the right and left nostril scores and ranges from 0 to 8, with higher scores indicating greater disease severity.

The primary assessment will be at Week 52. Baseline will be defined as the latest non-missing measurement collected prior to the first dose of study treatment (Section 4.1.2.1).

#### 4.2.1.2. Mean Individual VAS Symptom Scores

Every day each participant will be asked to indicate on a visual analogue scale (VAS) the severity of six nasal polyposis symptoms (one VAS for each symptom and one for symptoms overall) at its worst over the previous 24 hours. These VAS scores will include: (1) CCI [REDACTED]; (2) CCI [REDACTED]; (3) CCI [REDACTED]; (4) CCI [REDACTED]; (5) CCI [REDACTED] and (6) CCI [REDACTED] VAS score.

Participants will rate symptoms daily throughout the study on a VAS using an eDiary on a line with 101 individually selectable points ranging from 0 CCI [REDACTED] to 100 CCI [REDACTED]. The final VAS scores for inclusion in summary and analysis tables will be derived from the electronically captured score by dividing each score by 10, and therefore will range from 0 to 10 (reported to 1 decimal place).

Symptoms will be calculated as the mean of all relevant VAS score measurements during the 4 weeks prior to Week 52. Within the 4-week period each participant must have at least 4 days of non-missing diary data available within each given week (7 day) period for a week to be evaluable and must have at least 3 weeks of evaluable data for the 4-week period average to be derived. The mean VAS score over the last 7 days before the first dose of study treatment will be used to determine the baseline value of each VAS score (Section 4.1.2.2).

The individual VAS symptom score of nasal obstruction will be analysed as the co-primary endpoint in this study.

#### 4.2.2. Main Analytical Approach

The treatment effect to be estimated will be the comparison of mepolizumab 100 mg SC + SoC to placebo + SoC. The population of interest will be the entire trial population (patients meeting the study inclusion/exclusion criteria with a diagnosis of CRSwNP / ECRS) who are randomised and receiving study treatment (ITT analysis set).

The summary measure of treatment effect for the primary estimand of both co-primary endpoints will be the difference in mean scores between mepolizumab and placebo.

The main intercurrent events (ICEs) anticipated which may affect subsequent scores for the co-primary endpoints are:

- a) Premature discontinuation of study treatment unrelated to COVID-19 pandemic – to be handled using a treatment policy strategy. The study will continue collecting data for participants who prematurely discontinue from randomised treatment. Off-treatment data collected for these participants following treatment discontinuation will be included in the analysis.
- b) Changes in background medication or to start a prohibited medication (e.g. start INCS therapy where absent at baseline) unrelated to the COVID-19 pandemic – to be handled using a treatment policy strategy. These events will be captured as a protocol deviations and the study will continue treatment and to collect data for participants following this change in background medication / starting of a prohibited medication. Participants will not be expected to discontinue treatment or withdraw from the study.
- c) Premature discontinuation of study treatment or change in background medications or start of prohibited medication related to the COVID-19 pandemic (due to quarantines, site closures or other related issues) – to be handled using a hypothetical strategy. Data impacted by COVID-19 pandemic related events will not be included in the statistical analyses and will be treated as missing data.
- d) Surgery, which includes any procedure involving instruments resulting in incision and removal of tissue from the nasal cavity (e.g. polypectomy/FESS) – to be handled using a composite strategy by incorporating occurrence of the event into the definition of the endpoint. Specifically, participants who undergo surgery will be assigned the worst possible score for inclusion in the analysis of all subsequent visits (or 4-week periods) following surgery. Assessments taking place on the same day as surgery are assumed to have been carried out before the surgery.
- e) Course of systemic CS for CRSwNP / ECRS – to be handled using a treatment policy strategy. Data collected following a course of systemic CS for CRSwNP / ECRS will be included in the analysis where systemic CS will be considered as SoC treatment.
- f) Interruption to investigational product of 2 or more consecutive doses – to be handled using a treatment policy. These events will be recorded as protocol deviations and participants are expected to continue investigational product per-protocol after interruption. Data collected will be included in the analysis regardless of IP interruption.

This analysis will utilise the change from baseline in each of the co-primary endpoints where data for participants with surgery (prior to visit) are based on the worst possible score from the day after surgery onwards.

There are two expected sources of missing data namely, participants who withdrew early from study and participants who experienced an intercurrent event due to COVID-19 pandemic related restrictions. For the primary analysis, all missing data is assumed to be missing at random (MAR).

Analysis will be carried out using a mixed model repeated measures analysis with covariates of treatment group, baseline value, log of baseline blood eosinophil count, background INCS use (actual strata based on information related to INCS use recorded on eCRF), country and time point, plus interaction terms for time point by baseline value and time point by treatment group. Models will be checked for issues with convergence.

An unstructured covariance structure for the R matrix will be used by specifying 'type=UN' on the REPEATED line. The Kenward and Roger method for approximating the denominator degrees of freedom and correcting for bias in the estimated variance-covariance of the fixed effects will be used. The estimated means for each treatment group will be calculated from the model using the observed marginal distributions of the sample covariates (OM option in LSMEANS statement). Model-estimates of the absolute mean and mean change from baseline will be presented with corresponding standard errors for each treatment group by visit. Estimated treatment differences (Mepolizumab - Placebo) with corresponding 95% CIs and p-values will also be presented.

A cumulative distribution function (CDF) plot will also be provided for the change from baseline in both co-primary endpoints by treatment group: (1) endoscopic nasal polyps score at Week 52 and (2) mean nasal obstruction VAS score during the 4 weeks prior to Week 52.

When providing descriptive summaries of the co-primary endpoint data:

- 1) The diary scores for each 4-week period will be calculated as the mean of the scores reported between timepoints (e.g. Weeks 1-4, Weeks 5-8, Weeks 9-12, etc.). The 4-week period average will be derived as defined within Section [4.2.1.2](#). Further details of these 4-weekly periods will be defined within the OPS.
- 2) Participants with the intercurrent event of nasal surgery (as discussed above) will be assigned the worst possible score from the day after surgery onwards.

#### **4.2.3. Sensitivity Analyses**

For the primary estimand missing data for any reason is considered to be missing at random. A sensitivity analysis will be carried out whereby missing data due to premature withdrawal from the study will be imputed using off-treatment data and missing data due to occurrence of intercurrent events related to COVID-19 will be imputed as missing at random. An additional strategy will be implemented for missing data from participants who prematurely withdrew from the study. Off-treatment imputation assumes that future outcomes for those who withdraw can be predicted from a combination of participant characteristics, the participant's past observations and the patterns of response of participants who withdrew from investigational product but continued in the trial off-treatment. Off-treatment is defined as a visit occurring over 28 days after the last dose of interventional product.

For intercurrent events related to the COVID-19 pandemic, missing data is assumed MAR and will be imputed MAR. The imputation assumes that future missing outcomes for those who withdraw can be predicted from a combination of participant characteristics, the participant's past observations and the patterns of response of participants who remain in the trial without any intercurrent events related to COVID-19 (i.e. conditional on the data observed for each participant, their unavailable data are randomly missing). This corresponds to a standard likelihood analysis using MMRM.

Both imputation strategies will be implemented using multiple imputation.

Stepwise imputation methods will be implemented where imputations for a visit are conditioned on data from previous visits. Missing values will be imputed sequentially at post-baseline visits  $1, \dots, T$ . At a given visit  $t$  the imputation regression model will include both observed and imputed outcome values from previous visits  $1, \dots, t-1$ , baseline score, log of baseline blood eosinophil count, background INCS use, country and treatment at visit  $t$ . Both observed and imputed outcome values from previous visits will be used in the regression model.

The treatment covariate at visit  $t$  will be equal to the randomised treatment if the participant was still on-treatment or a generic 'off-treatment' if the participant had already discontinued from treatment. For participants who had already discontinued from the study at visit  $t$ , missing values will be imputed based on the regression model and assuming those observations are off-treatment.

Analysis will be performed using mixed model repeated measures as described for the primary analysis. For off-treatment imputation, the results will be combined across at least 2000 imputations using Rubin's rules [Rubin, 1987].

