1.2. Schema

1.3. Schedule of Activities (SoA)

	Procedure	Pre-screening ¹	Screening ¹	Treatment															
				0	1	2	3	4	5	6	7	8	9	9a	10	11	12	13	14
Visit		0	up to 28 ±7 days prior to Day 1	1	29	57	85	113	141	169	197	204 (±1day)	225	253	281	309	337	365	28 ±7 days post last dose
Study Day (visit window ±7 days)				0	4	8	12	16	20	24	28	29	32	36	40	44	48	52	
Week																			
Screening/baseline	Informed consent	X																	
	Blood collection for eosinophils eligibility confirmation (if required) ²	X																	
	Inclusion and exclusion criteria		X																
	Demography		X																
	Full physical exam including height and weight		X																
	Medical history (includes substance usage and family history of premature CV disease CRSwNP/ECRS and asthma therapy, asthma and exacerbation history and concomitant medications)			X															
	SAE Review			X															
	History of HIV and Hep B, Hep C screen				X														
	Past and current medical conditions including cardiovascular medical history					X													
	History of systemic CS use for NP					X													
	History of NP surgery						X												

	Procedure	Pre-screening ¹	Screening ¹	Treatment																	
				0	1	2	3	4	5	6	7	8	9	9a	10	11	12	13	14	15	
Visit	Study Day (visit window ± 7 days)		up to 28 ± 7 days prior to Day 1	0	1	2	3	4	5	6	7	8	9	9a	10	11	12	13	14	15	IP DISC / EW Visit
Study Day (visit window ± 7 days)						1	29	57	85	113	141	169	197	204 (± 1 day)	225	253	281	309	337	365	28 ± 7 days post last dose
Week						0	4	8	12	16	20	24	28	29	32	36	40	44	48	52	
	Parasitic screening ³					X															
	Screening 12-lead ECG					X															
	Screening Vital signs					X															
	Assessment of endoscopic NP score ¹¹					X															
	Assessment of VAS for NP symptoms including Overall VAS ⁶					X															
	Assessment of Screening CT ⁴					X															
	Screening Laboratory assessments: Haematology (including blood eosinophils) and chemistry (including liver chemistries)					X															
	Screening Urinalysis					X															
	Urine pregnancy test (WOCBP only) ⁵					X															
	Dispense and Train in the use of eDiary ⁶					X															
	Register visit	X	X	X	X	X	X	X	X	X	X	X	X		X	X	X	X	X	X	
	Randomisation					X															
	Genetics sample ⁷														X						
Efficacy	Assessment of NP Surgery					X	X	X	X	X	X	X	X		X	X	X	X	X	X	

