6.1. Study Intervention(s) Administered

Study intervention or treatment is defined as any investigational treatment(s), marketed product(s), placebo, or medical device(s) intended to be administered to a study participant according to the study protocol.

A liquid formulation of mepolizumab will be provided as pre-filled syringes in a safety syringe device (SSD) for this study. The liquid formulation has a distinct advantage over the lyophilised product as it does not require reconstitution, and the devices (upon commercial registration) will simplify and facilitate administration.

There will also be a matched safety syringe with placebo. Both active and placebo drug products are stored at 2-8°C condition, protected from light.

The study consists of up to 17 visits with a maximal total treatment duration of approximately 52 weeks and maximum study duration of approximately 56 weeks. Screened participants will enter a 4 weeks run-in period, followed by up to 52 weeks double-blind treatment period.

Participants who are successfully enrolled into the study will be randomised in a 1:1 ratio into one of two treatment groups, receiving a total of thirteen doses (one every four weeks):

- Group 1: 100 mg SC of mepolizumab on top of SoC
- Group 2: Placebo SC on top of SoC

The end of study assessments for each individual participant will be performed at Visit 15 (Week 52), 4 weeks following the last dose of IP.

Study Treatment	
Product name:	Mepolizumab Injection, 100 mg/mL
Device:	Safety syringe
Formulation description:	100 mg/mL mepolizumab with sodium phosphate, citric acid, sucrose, Disodium EDTA, Water for Injection and polysorbate 80
Dosage form:	Sterile, liquid formulation
Unit dose strength(s)/Dosage level(s):	100 mg/mL; 1.0 mL (deliverable)
Route of Administration	SC injection
Dosing instructions for HCP:	SC dose in thigh, abdomen or upper arm every 4 weeks
Dosing instruction for self-injection:	SC dose in thigh or abdomen every 4 weeks
Physical description: mepolizumab	Clear to opalescent, colourless to pale yellow to pale brown sterile solution for SC injection in a single-use, safety syringe
Physical description of injection device:	Single use, disposable safety syringe device assembled with a pre-filled syringe containing mepolizumab solution. A plastic needle cover shields the needle before and after injection to minimise the potential for needle stick injuries.

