7.1.4. IP Discontinuation Visit

Prematurely discontinuation of study treatment will be defined as any participant who is randomised to blinded medication and, for any reason, does not receive study treatment at Visit 14 (Week 48).

A participant may discontinue from study treatment at any time at his/her own request, or at the discretion of the investigator. Participants who discontinue from study treatment prematurely (for any reason) should, where possible, continue to be followed-up as per protocol until the completion of the Week 52 Visit assessments.

Participants that discontinue from study treatment should return to the clinic 4 weeks after the last dose for an IP Discontinuation Visit. If possible, at the IP Discontinuation Visit, the following evaluations and procedures should be completed and recorded in the eCRF as required:

- Concomitant medication assessment
- Adverse event assessment
- 12 -lead ECG
- Physical examination (recorded in source documents only)
- Vital signs
- Collect/review electronic diary
- Urine pregnancy test - for all WOCBP
- Assessment of endoscopic nasal polyp score
- Assessment of surgery
- Assessment of systemic CS use
- Assessment of INCS use
- Assessments of symptoms
- Assessment of HRQoL
- WPAI
- PK (Japan and China only)
- Lab assessments including liver chemistry and immunogenicity

- CT scan
- Assessment of asthma exacerbations
- Collection of eDiary
- Access the RAMOS NG to report participant's IP discontinuation visit from the study

After completion of the IP Discontinuation Visit, in cases where the participant cannot attend subsequent study visits in person telephone visits may be performed.

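### SAP 4.2.3 gives two conflicting rules for off-treatment status, and the 28-day rule, read literally, relabels fully dosed completers who attend Week 52 a day or more late

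*SAP*

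**What the plan says.** SAP 4.2.3 imputes missing data after study withdrawal by multiple imputation, one visit at a time. Each visit's regression includes a treatment covariate with a generic off-treatment level, and withdrawn participants are imputed at that level. The section says three things about the level:

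- The reference is the "patterns of response of participants who withdrew from investigational product but continued in the trial off-treatment".
- The next sentence defines the term: "Off-treatment is defined as a visit occurring over 28 days after the last dose of interventional product".
- The paragraph on the covariate keeps randomised treatment while the participant is on treatment, and otherwise uses "a generic 'off-treatment' if the participant had already discontinued from treatment".

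On timing, Protocol 6.1 says that end-of-study assessments "will be performed at Visit 15 (Week 52), 4 weeks following the last dose of IP". The Schedule of Activities puts the Week 48 dose on Day 337 and Week 52 on Day 365, with ±7-day windows. Protocol 4.4 counts anyone dosed at Week 48 as having completed treatment. Protocol 7.1.4 defines premature discontinuation as not receiving that dose.

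**The concern.** The first and third statements define off-treatment by what happened to the participant. The second defines it by elapsed days and does not restrict itself to people who stopped. Its cut-off equals the scheduled gap from last dose to primary assessment, so it leaves no room for a late visit. A participant with all 13 doses who attends on day 29 meets the definition of off-treatment, although the protocol says that person completed treatment.

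This matters because the analysis exists to predict withdrawals from people who stopped product but stayed in the trial. That group is likely to be small, so a modest number of mislabelled completers could outnumber it at the Week 52 step. The 28-day sentence is also the section's only explicit definition of the term, so a programmer may well code from it. SAP 4.2.4 holds supplementary estimands for steroid courses and surgery, not a second missing-data analysis.

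**Working it through.** **Plan's own figures.** The SAP states no share of participants classed as off-treatment, so there is none to reproduce. The inputs borrowed from SAP 5 do reproduce: for nasal polyp (NP) score, SE = 1.82 × √(2/80) = 0.288, and the noncentral t with 158 df at a difference of 1.00 gives 93.2% power and a critical difference of 0.568 (stated: 93.2% and 0.57).

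**Step 1: share of completers past day 28.** The nominal gap is 365 − 337 = 28 days. With windows of −7 to +7 there are 15 possible days per visit. The visit-day distribution is not in the documents, so it is varied. Let m be the probability that a visit falls on its nominal day, with the rest spread evenly.

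- Week 52 date measured from the actual Week 48 dose: (1 − m)/2.
- Both visits varying independently: [1 − m² − (1 − m)²/14]/2.

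| Assumed spread | Share over 28 days |
|---|---|
| Even (m = 1/15) | 7/15 = 46.7% (both) |
| Triangular | 43.8-45.8% |
| Even, endoscopy 0-3 days early | 37.8% |
| m = 0.5 | 25.0-36.6% |
| m = 0.75 | 12.5-21.7% |
| m = 0.9 | 5.0-9.5% |

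The 12-47% range therefore covers spreads in which at least a quarter of visits miss the nominal day. Under the discontinuation rule the share is 0%.

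**Step 2: make-up of the Week 52 off-treatment group.** Let W be withdrawals and R those who stopped product but stayed, both assumed. Mislabelled completers = f × (160 − W − R), and their share of the group is mislabelled/(mislabelled + R).

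- W = 16, R = 8, f = 0.467: 0.467 × 136 = 63.5; 63.5/71.5 = 89%.
- W = 16, R = 16, f = 0.467: 0.467 × 128 = 59.8; 59.8/75.8 = 79%.
- W = 16, R = 8, f = 0.125: 17; 17/25 = 68%.
- W = 16, R = 16, f = 0.125: 16; 16/32 = 50%.

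Over R = 2-16 and W = 8-16 the share is 79-97% at f = 0.467 and 50-90% at f = 0.125. With 1:1 allocation about half of those mislabelled are on placebo.

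**Step 3: apparent precision.** Ignoring other covariates, the SE of the off-treatment coefficient against on-treatment placebo is proportional to √(1/n_off + 1/n_placebo). With W = 16:

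- R = 8: √(1/8 + 1/68) = 0.374 under the discontinuation rule. Under the clock rule it is √(1/71.5 + 1/36.2) = 0.204 at f = 0.467 (45% smaller) and √(1/25 + 1/59.5) = 0.238 at f = 0.125 (36% smaller).
- R = 16: √(1/16 + 1/64) = 0.280, against √(1/75.8 + 1/34.1) = 0.206 (26% smaller) and √(1/32 + 1/56) = 0.222 (21% smaller).

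Simulation of the stepwise imputation gave 25-47%.

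**Step 4: effect on imputed values and the treatment difference.** Large-sample simulation: NP effect 1.0, SD 1.82, 10% withdrawn, 5% retained off treatment, effect lost over two visits, f = 0.467. Means are for withdrawn participants at Week 52, discontinuation rule → clock rule.

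| Correlation | Mepolizumab | Placebo | Treatment difference |
|---|---|---|---|
| Autoregressive 0.8 | −0.207 → −0.274 | 0.219 → 0.139 | −0.894 → −0.892 |
| Autoregressive 0.5 | −0.115 → −0.235 | 0.077 → −0.045 | −0.870 → −0.869 |
| Exchangeable 0.6 | −0.176 → −0.458 | 0.174 → −0.081 | −0.881 → −0.883 |

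The shift is 0.07-0.28 towards improvement and similar in both arms, because off-treatment is one level shared by both. The difference therefore changes by roughly the shift times the gap in withdrawal proportions: with 20% against 8%, 0.28 × 0.12 = 0.03. In simulated trials of 160 the change had a median of about 0.02 with equal withdrawal and 0.03 with 8% against 20%; the 90th percentiles were about 0.04 and 0.11. The SE of the treatment difference was at most about 3% too small.

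**The case against.** The strongest reply is that the section, read as a whole, never lets completers in. The sentence before the definition names people who withdrew from product, the covariate paragraph requires discontinuation, and Protocol 4.4 and 7.1.4 class Week 48-dosed participants as completers. On that reading the 28 days only mark when a discontinued participant's visits begin to count. SAP 1 also sends further data-handling conventions to the Output and Programming Specification, which is not available here. This stands to a point: misclassification is not settled. But the definition carries no such restriction, and nothing says which rule governs.

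Four stronger inferences are tempting and are not supported:

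- That nearly half of completers will be relabelled. This needs visit dates spread evenly over the window, and the documents give no distribution.
- That withdrawals would be imputed mainly from mepolizumab-treated people. About half of those mislabelled are on placebo, only the Week 52 step is affected (completers' earlier visits precede their last dose), and the regression also conditions on each participant's earlier scores and baseline covariates.
- That a deliberately pessimistic test is being softened. Protocol 9.4.1 says only that the analysis examines how handling choices affect the result, and the shift largely cancels between arms.
- That every 4-weekly visit is affected because last dose could mean the most recent dose. That is a strained reading and nothing here rests on it.

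**Conclusion.** The concern holds as an unresolved contradiction inside SAP 4.2.3, with one of its two rules wrong as written for participants who complete treatment. If that rule is coded, some 12-47% of completers of both arms are mislabelled at Week 52 and could make up most of the reference group. Imputed NP scores for withdrawals move by about 0.1-0.3 points, and the off-treatment coefficient appears roughly 20-47% more precise (in SE) than the true off-treatment participants can support.

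The effect on the estimate is small: about 0.02 in the median, against an assumed effect of 1.00, and larger if withdrawal is unbalanced. The primary analysis is untouched and no change in the trial's conclusion is claimed. Visit spread, withdrawal, off-treatment retention and speed of loss of effect are all assumptions. Only NP score was simulated. The nasal obstruction VAS co-primary is a 4-week diary mean, and the SAP does not say how a visit-based status applies to it.

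**What to change.** Replace the 28-day sentence in SAP 4.2.3 with a statement that:

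- off-treatment status follows premature discontinuation of product, as in Protocol 7.1.4 and the SAP's own covariate paragraph;
- participants dosed at Week 48 keep their randomised treatment at Week 52;
- any day cut-off applies only to participants who have discontinued;
- status is assigned to each 4-week diary period of the VAS co-primary by a stated rule.

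Simply widening the cut-off to 35 days is not a good substitute. It would add a third rule and would count a discontinued participant's visit on days 29-35 as on treatment, against the covariate paragraph.

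The cost is a short SAP edit and the matching derivation, with no new data. It should be settled before unblinding so that the choice is not left to the analyst. The downside is that the true off-treatment group is small, so its coefficient will be less precise, which is the honest position.
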